1.2. Rationale

In our CLlIgAN study, we have planned to evaluate:

- (i) The effect of early start corticosteroid therapy combined with RASBs (experimental arm) versus RASBs alone in IgAN patients with active renal lesions (AClIgAN) who will receive corticosteroids after 4 months of RASBs (standard care) in presence of persistent proteinuria ≥ 0.5 g/24 hours and eGFR ≥ 30 ml/min/1.73 m² (control arm).
- (ii) The effect of SGLT2i (dapagliflozin) combined with RASBs (experimental arm) versus corticosteroids combined with RASBs (control arm) in IgAN patients with chronic or moderate renal lesions (CHRONlIgAN) after a run-in phase of 4 months in which they will receive RASB therapy alone (standard care).

In both studies patients enrolled in the control arms will be treated according to the evidence-based recommendations (standard care) provided within the KDIGO guidelines.

In conclusion, we would like to evaluate the effect of early start corticosteroids in IgAN patients with active renal lesions (AClIgAN) and to spare corticosteroids therapy in IgAN with chronic or moderate renal lesions (CHRONlIgAN) administering Dapagliflozin.

We would also provide earlier ESKD risk prediction by using our tool DialCheck (32).

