
Endpoints
	
Primary endpoint:
 
 • Between-arms difference in proteinuria reduction within 4 months and in non-responders within 8 months in ACiGaN study. • Between-arms difference in proteinuria reduction within 10 months in CHRONiGaN study. 
Secondary endpoints:
 
 • eGFR slope calculated as mean of individual slope obtained from individual linear regression of eGFR overtime (3 years); • eGFR decline > 40 % from the baseline value; • composite end point: GFR decline > 40%, ESKD (defined as long-term GFR ≤ 15 ml/min/1.73m² for more than three months or need for maintenance dialysis or kidney transplantation) or death due to kidney disease; • absolute difference between last GFR value and baseline GFR; • stable renal function defined as a decline in GFR ≤ 5 ml/min/1.73m² at the end of three years follow- up; • mean annual change in the slope of the reciprocal of serum creatinine concentration;

	
 time-averaged proteinuria (TA-P) calculated as the weighted mean of all post-randomisation measurement, with weights representing the time elapsed since the previous measurement; proteinuria slope, calculated as a mean of individual slope, obtained from individual linear regression of daily proteinuria overtime (3 years); complete remission of proteinuria defined as achievement of urinary protein level ≤ 0.2 g/day or a urinary protein-to-creatinine ratio ≤ 0.2 g/g; partial remission of proteinuria defined as achievement of a urinary protein reduction $\geq 50\%$ or greater compared with the baseline value.
Number of Sites	Over 30
Number of patients	
432 patients:
 
 132 patients (66 patients per group, including a 10% dropout rate, in the ACiGaN trial) 300 patients (150 patients per group, including a 10% dropout rate, in the CHRONiGaN trial)

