
Study Products
	
Methylprednisolone succinate and prednisone (Corticosteroids, CS) Dapagliflozin (Sodium-glucose cotransporter 2 inhibitor, SGLT2i)

Treatments
	
ACiGaN Study
 
IgAN Active renal lesions
 
Experimental arm: Corticosteroids + RASBs (4 months) → RASBs (4 months) → RASBs (28 months)
 
Control arm (KDIGO): RASBs (4 months) → RASBs + Corticosteroids (4 months) → RASBs (28 months)
 <hr/> 
CHRONiGaN Study
 
IgAN Chronic renal lesions Moderate renal lesions
 
Experimental arm: RASBs (4 months) → RASBs + Dapagliflozin (6 months) → RASBs + Dapa (26 months)
 
Control arm (KDIGO): Run-in → RASBs + Corticosteroids (6 months) → RASBs (26 months)
 
Patients will be randomized separately in each trial (allocation 1 to 1 ratio). Stratified randomization will be done by age and sex in renal centers.
 
ACiGaN trial
 
Experimental arm: Early corticosteroids therapy combined with RASBs followed by RASBs treatment.
 
Control arm (standard care): RASBs treatment followed by corticosteroids combined with RASBs and then only RASBs.
 
CHRONiGaN trial
 
Experimental arm: RASBs therapy followed by Dapagliflozin combined with RASBs.
 
Control arm (standard care): RASBs therapy followed by Corticosteroids combined with RASBs and then RASBs alone

Sample Size and Statistics
	
ACiGaN. Data from the literature have shown a difference in renal survival between corticosteroids and controls when the researchers assumed a difference of 50% in the primary end point (i.e., in the between-arms difference of delta 24 hour proteinuria from base-line to 6 months) as clinically relevant. Therefore, we assume that a mean delta proteinuria from base-line to 6 months in patients treated with RASBs alone (control arm) is 0.6 ± 1.0 g/24 hours (\pmSD) versus a mean delta proteinuria 1.2 ± 1.0 g/24 hours (\pmSD) from base-line to 6 months in patients treated with RASBs and corticosteroids (experimental arm). Based on these assumptions, we calculated a sample size of 132 patients (66 patients per group including a 10% dropout rate) for a power of 90%, a two-sided significance level of 0.05 and 3 years

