3. TRIAL DESIGN

This project encompasses two prospective, multicentre, open-label randomized controlled clinical trials (RCTs) of IgAN patients (CLlGaN) based on the kidney biopsy report (*Figure 1*).

Stratified randomization will be done by age and sex in renal centers.

[figure not shown]

Figure 1

ACiGaN TRIAL

Patients with active renal lesions (E1 and/or C1) in the presence of $GFR \geq 30$ ml/min/1.73 m² and proteinuria ≥ 0.5 g/24 hours will be randomized into two arms:

- 1) corticosteroids combined with RASBs for 4 months followed by RASBs alone (experimental arm);
- 2) RASBs alone for 4 months followed by the combination corticosteroids and RASBs for 4 additional months and then only RASBs (standard care) as suggested by KDIGO guidelines (5).

Participants assigned to the experimental arm will receive by 2 weeks from the kidney biopsy (pulse) methylprednisolone (SOLU-Medrol) 500-1000 mg in the first day and then 50% of dose in the next two days followed by oral prednisone (0.5 mg/kg/bw) on alternate days until the end of the month. This treatment will be repeated for three consecutive months. After three months, participants will gradually reduce oral prednisone, in the course of four weeks. Next, they will receive RASBs alone.

The daily dose of methylprednisolone will be individualized (15 mg/kg), based on the ideal body weight. The drug will be administered in a single dose intravenously for 30-60 min. To avoid obesity and diabetes corticosteroids will be administered only in the morning.

This is a parallel group, two arm, superiority trial with 1:1 allocation ratio.

As per standard care RASB therapy will be titrated to its maximum labelled or tolerated dose as anti-proteinuric effect in every patient.

Rationale of the study design

Corticosteroids at high dosage have been administered in RCTs of IgAN (18,41) independent of the type of renal lesions despite empiric evidence from clinical practice and strong and consistent evidence from observational studies that the lesions identified at kidney biopsy may play a role in the response to treatment. Our aim is to evaluate the benefit of early pulse therapy combined with oral prednisone only in IgAN patients with active renal lesions. In our protocol, we have excluded intensive immunosuppressive therapy (CS+CYP/AZA/MMF) because RCTs have demonstrated that the potential benefits-harms trade off is in favour of the harms (42).

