To our knowledge, this is the first study in which corticosteroids are administered immediately after the kidney biopsy in IgAN patients with active renal lesions. Based on the existing evidence from randomized clinical trials, the KDIGO guidelines suggest in those cases: RASBs for 3-6 months and then corticosteroids in presence of persistent proteinuria and $GFR >30$ ml/min/1.73 m². This therapeutic approach, although supported by evidence, may be a challenge based on empiric clinical knowledge supported also by findings of cohort studies. This demonstrates that after 3-6 months active renal lesions become chronic and consequently no association may be found between exposure to corticosteroids and clinical response for IgAN patients. In our randomized clinical study we compare the standard approach proposed by KDIGO guidelines (RASBs for 3-6 months followed by corticosteroids) vs a novel approach consisting of early corticosteroid therapy combined with RASBs from the beginning.

CHRONIgAN TRIAL

Patients with chronic (T1,2) or moderate renal lesions (M0,1; S0,1, E0, C0, T0) will be enrolled in a two-arm trial with 1:1 allocation ratio to compare Dapagliflozin combined with RASBs (experimental arm) versus corticosteroids combined with RASBs (control arm) after 4 run-in months of RASBs treatment. The enrolled patients will have proteinuria ≥ 0.5 g/day and GFR ≥ 30 ml/min/1.73 m².

Participants will receive study treatments by 4 weeks from the kidney biopsy.

Patients assigned to the experimental arm will receive RASBs therapy (4 run-in months) followed by Dapagliflozin (10 mg /day orally) combined with RASBs for a total of 32 consecutive months. Patients assigned to the control arm will receive RASBs therapy (4 run-in months) followed by oral corticosteroids therapy (prednisone) for six months (0.4 mg/kg body weight for 2 months and then gradual reduction of 5 mg/day for 4 months) and then RASBs alone for a total of 36 consecutive months.

This is a parallel group, two arm, superiority trial with 1:1 allocation ratio.

Rationale of the study design

We decided the combination Dapagliflozin and RASBs because recently, SGLT2is were administered in patients with type 2 diabetes and in other participants with CKD (some of them were affected by IgAN) (29-31). In these studies, the effect of SGLT2is was compared with a placebo.

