4.3 Interventions

4.3.1 Study treatments (dosage and rationale)

Study drugs (already been placed on the market as authorized medicinal products) will be not supplied by the study Sponsor and will be administered according their labelling and no additional labelling will be required to ensure subject safety and the reliability and robustness of data generated in this clinical trial.

For all information about study drugs, please refer to their respective Summary of Product Characteristics (SmPCs).

RASBs

Patients will receive treatment with renin-angiotensin system blockers, RASBs (either angiotensin-converting enzyme inhibitor, ACEi, or angiotensin II receptor blocker, ARB) as per clinical practice, according to the current KDIGO guidelines.

For example, Ramipril will be administered at dosage of 5 mg x 2 times per day (8.00-20.00) in patients with blood hypertension. Then, it will be increased of 2.5 mg x 2 per day every three days until the reduction of hypertension and proteinuria.

In patients with normal arterial blood pressure Ramipril will be administered at dosage of 2.5 mg x 2 times a day

In patients no tolerant to Ramipril, a sartan will be administered, i.e. Losartan 12.5 mg x 2 times a day. A gradual increase of 6.25 mg (two times a day) will be done to reduce proteinuria.

Rationale: RASBs will be administered to reduce blood pressure at glomerular level and proteinuria (39,40).

Dapagliflozin

The drug will be administered at dosage of 10 mg per day as reported in other randomized clinical trials in which Dapagliflozin has been administered in combination with RASBs (29,31).

Rationale: To reduce blood pressure at glomerular level and proteinuria.

Corticosteroids

AClIgAN trial

Methylprednisolone will be administered at dosage of 15 mg/kg body weight until the dosage of 1 gr in the first day and 50% reduced dose in the other two days and then Prednisolone at dosage of 0.5 mg/kg body weight at alternate days will be administered until the end of the month. This treatment will be repeated for 3 consecutive months. After 3 months, prednisone will be gradually reduced of 25% of the dosage every week until the end of treatment (4 weeks).

Rationale: To care the active renal lesions represented by endocapillary and extracapillary glomerular lesions. This treatment has been used in other clinical trials of IgAN (12,18,43).

CHRONlIgAN trial

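### ACiGaN control arm: corticosteroids at month 4 depend on proteinuria and eGFR in section 1.2, but go to every control in the arm definitions

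*Protocol*

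**What the plan says.** **ACiGaN, conditional text.** Section 1.2 describes controls as patients "who will receive corticosteroids after 4 months of RASBs (standard care) in presence of persistent proteinuria" of at least 0.5 g/24 h, together with eGFR of at least 30. The synopsis primary endpoint points the same way: "Between-arms difference in proteinuria reduction within 4 months and in non-responders within 8 months in ACiGaN study". Section 4.4 lists months 4 and 8 without the non-responder restriction.

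**ACiGaN, unconditional text.** The synopsis defines the control arm as "RASBs treatment followed by corticosteroids combined with RASBs and then only RASBs". Section 3 has "RASBs alone for 4 months followed by the combination corticosteroids and RASBs for 4 additional months", then RASBs only, and describes this "as suggested by KDIGO guidelines (5"), where 5 is the 2021 edition. The control row of Figure 2A shows the same sequence without a branch.

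**ACiGaN, dosing text.** Section 4.3.1 gives the regimen, beginning "Methylprednisolone will be administered at dosage of 15 mg/kg body weight until the dosage of 1 gr in the first day". It names no arm and no order of treatments.

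**KDIGO.** Section 1.2 says of both trials: "In both studies patients enrolled in the control arms will be treated according to the evidence-based recommendations (standard care) provided within the KDIGO guidelines". Section 1.1 reports KDIGO as offering corticosteroids after supportive therapy when proteinuria exceeds 1 g/day and eGFR exceeds 50, and no immunosuppression at eGFR 30 to 50 or below 30. It says the 2021 edition confirmed this. The ACiGaN rationale in section 3 reports KDIGO as suggesting corticosteroids after 3 to 6 months of RASBs when proteinuria persists and GFR exceeds 30.

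**CHRONiGaN.** Section 3 reads "Patients assigned to the control arm will receive RASBs therapy (4 run-in months) followed by oral corticosteroids therapy (prednisone) for six months", with no response criterion. The synopsis, Figure 2B and the dosing sentence in section 4.3.1 agree. Only the rationale sentence in section 4.3.1 limits the course to patients who did not respond to RASBs alone, a term the protocol does not define.

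**The concern.** Who receives study drug has to be readable from the treatment sections. Here the only explicit trigger sits in the rationale, and the arm definitions neither repeat it nor refer to it. Two sites could follow the protocol in good faith and treat the same control differently. One would give a pulse corticosteroid course to a patient already below 0.5 g/24 h, or to one whose eGFR is below 30; the other would not.

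Patients below 0.5 g/24 h are to be expected, because section 3 has RASBs titrated to bring proteinuria to 0.5 g/day or less. Adherence becomes ambiguous too. An untreated responder complies with section 1.2 but departs from section 3, and section 6.5 builds a secondary population on persistence with the investigational drugs to months 4 and 8.

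**Working it through.** **Step 1. The rule applied to a control at month 4.**

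| Proteinuria at t4 | eGFR at t4 | Section 1.2 | Synopsis, section 3, Figure 2A |
|---|---|---|---|
| ≥0.5 g/24 h | ≥30 | corticosteroids | corticosteroids |
| <0.5 g/24 h | ≥30 | RASBs alone | corticosteroids |
| ≥0.5 g/24 h | <30 | RASBs alone | corticosteroids |
| <0.5 g/24 h | <30 | RASBs alone | corticosteroids |

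The texts agree only in the first row. In the third and fourth rows, both of the protocol's accounts of KDIGO would also withhold corticosteroids, so the arm definitions stand alone.

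**Step 2. Which comparisons are touched.** The step comes after month 4, so the month-4 contrast is the same under either reading. The control course runs from month 4 to month 8. Under the arm definitions, all controls have had it by month 8. Under section 1.2, the arm is a mixture of treated patients and patients kept on RASBs. That difference carries into the 3-year endpoints.

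**Step 3. Exposure per patient.** This assumes that the section 4.3.1 regimen applies to the control course, which that section does not say.
- Per cycle: 1 + 0.5 + 0.5 = 2 times the first-day dose.
- Three cycles: 3 × 2 = 6 times the first-day dose.
- First-day dose 500 to 1000 mg (section 3; the cap in section 4.3.1 is 1 g): 6 × 0.5 = 3 g to 6 × 1.0 = 6 g intravenously, plus alternate-day oral steroid.

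**Step 4. Scale.** The protocol gives neither the share of patients responding to RASBs nor the eGFR or proteinuria distribution at month 4. The number affected cannot be derived. Each 10% of controls is 0.10 × 66 = 6.6, about 7 patients.

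**Step 5. The two KDIGO accounts.**

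| Patient after the RASB period | Section 1.1 | Section 3, ACiGaN rationale |
|---|---|---|
| eGFR 30 to 50 | no immunosuppression | corticosteroids if proteinuria persists and GFR >30 |
| Proteinuria 0.5 to 1 g, eGFR >50 | below the 1 g/day threshold | no threshold given, so eligible if this counts as persistent |

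Both trials enrol at eGFR ≥30 and proteinuria ≥0.5 g (sections 4.2.1.1 and 4.2.1.2), so patients in these ranges can be in the control arms. Section 1.1 ties its account to the 2021 edition, the same reference that section 3 cites for the ACiGaN control sequence.

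**Step 6. Sample size.** It is not in dispute. With a difference of 0.6, SD 1.0, two-sided 0.05 and 90% power, 2 × (1.960 + 1.282)² / 0.6² = 58.4, so 59 per arm. Then 59 / 0.9 = 65.6, so 66 per arm and 132 in total, as stated.

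**The case against.** The strongest reply is that the arm definitions are shorthand. Section 3 ties the control sequence to KDIGO, and its own ACiGaN rationale then describes KDIGO as conditional on persistent proteinuria and GFR above 30. The synopsis endpoint's mention of non-responders fits that reading. Figure 1 and the synopsis flow chart cannot be seen in the text at hand and might show a month-4 branch.

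Part of this stands. The conditional reading is the likelier intention, and section 3 is not wholly silent. But its rationale describes a guideline, gives no proteinuria threshold and instructs no one. A branch in a figure would still contradict the written arm definitions and the Figure 2A row.

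Some stronger readings are tempting, but the protocol does not support them:
- **That section 4.3.1 also contradicts the trigger.** It is a dosing regimen, silent on arm, order and condition.
- **That the KDIGO conflict leaves the ACiGaN trigger open.** Section 1.2 states the thresholds outright. The conflict weakens the standard-care label, and which account is right cannot be checked from the protocol.
- **That the CHRONiGaN comparator is equally ambiguous.** One rationale phrase stands against uniform treatment text, so month 10 is at risk only if a site acts on that phrase.
- **That the primary result is biased in a known direction.** Nothing in the protocol allows a direction or a size to be derived.

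**Conclusion.** The point holds as an internal contradiction about who receives a study drug, and it should be fixed. The ACiGaN control rule at month 4 is conditional in section 1.2 and unconditional in the synopsis, section 3 and Figure 2A. It affects the safety of controls with proteinuria below 0.5 g/24 h or eGFR below 30, and it affects what the control arm represents at month 8 and over 3 years. The month-4 comparison is untouched. The number of patients is unknown, and the 3 to 6 g exposure rests on applying the section 4.3.1 regimen to controls.

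The KDIGO conflict is secondary: on the section 1.1 account, the standard-care label is not supported for controls who, after the RASB period, have eGFR 30 to 50 or proteinuria 0.5 to 1 g. The CHRONiGaN phrase is minor.

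**What to change.** 1. **ACiGaN trigger.** State in the synopsis, sections 3 and 4.3.1 and Figure 2A that controls receive corticosteroids after month 4 only if proteinuria is ≥0.5 g/24 h and eGFR ≥30 at t4, and otherwise continue RASBs alone.
2. **Month-8 analysis.** Keep all randomised patients in the intention-to-treat analysis. Remove the non-responder restriction from the synopsis endpoint: section 4.4 does not carry it, and it would select patients on a post-randomisation response.
3. **KDIGO.** Give one account and state where each control arm departs from it. The unconditional CHRONiGaN course is one such departure, since both accounts require proteinuria to persist.
4. **CHRONiGaN.** Align the rationale phrase in section 4.3.1 with the unconditional treatment text.

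The cost is an amendment of wording. No visit or test is added, because Figure 2A already schedules proteinuria and eGFR at t4. The ACiGaN thresholds are already written in section 1.2 and equal the entry criteria in section 4.2.1.1. Aligning the CHRONiGaN phrase changes no treatment.

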1.3. Study products

Corticosteroids

Methylprednisolone (SOLU-MEDROL)

Methylprednisolone is a potent anti-inflammatory steroid. It has a greater anti-inflammatory potency than prednisolone and even less tendency than prednisolone to induce sodium and water retention. Its anti-inflammatory activity is at least five times that of hydrocortisone.

Methylprednisolone sodium succinate has the same metabolic and anti-inflammatory actions as methylprednisolone. When given parenterally and in equimolar quantities, the two compounds are equivalent in biologic activity. The relative potency of methylprednisolone sodium succinate and hydrocortisone sodium succinate, as indicated by depression of eosinophil count, following intravenous administration, is at least four to one.

Among other uses, it is indicated to induce remission of active renal lesions and proteinuria in IgAN patients (13,14,18) and in other renal diseases as idiopathic nephrotic syndrome (33,34) and lupus nephritis (35).

Prednisone

Prednisone, while exhibiting the typical glucocorticoid steroid profile, does differ from cortisone, from which it derives by dehydrogenation in position 1, 2 of the molecule, due to its ability to increase (on average 4 times compared to cortisone) all those pharmacological activities connected

with the antireactional properties of this class of compounds. Prednisone does not possess by itself a biological activity, but it becomes active in the organism as it undergoes, by hepatic reductases that reduce the ketone in position 11 to hydroxyl, a rapid conversion to prednisolone which represents the metabolite activated steroid. Under normal conditions this process takes place quickly and totally in the liver, so much so that prednisone and prednisolone can be found to be pharmacologically equivalent.

Studies conducted in different experimental models, in addition to demonstrating the remarkable anti-inflammatory activity of the cortisone, indicated that the prednisone is able to influence glyconeogenesis, to stimulate the deposition of hepatic glycogen, to determine an eosinopenizing effect, to prolong survival time in adrenalectomised animals, to protect rats from acute egg white poisoning, to inhibit weight growth and to antagonize the experimentally induced alterations in the endothelium of veins and capillaries. Finally, the experiences carried out on hydro-mineral excretion have shown that administering dose treatments of prednisone cause a beneficial increase in diuresis and elimination of sodium, without stimulating urinary excretion of potassium.

Prednisone has been administered in IgAN patients (10-12), in proliferative primary and secondary glomerulonephritis (36) to reduce the inflammatory process at glomerular level.

Dapagliflozin (SGLT2i)

Dapagliflozin is a highly potent (K_i : 0.55 nM), selective and reversible inhibitor of SGLT2.

Inhibition of SGLT2 by dapagliflozin reduces reabsorption of glucose from the glomerular filtrate in the proximal renal tubule with a concomitant reduction in sodium reabsorption leading to urinary excretion of glucose and osmotic diuresis. Dapagliflozin, therefore, increases the delivery of sodium to the distal tubule which increases tubuloglomerular feedback and reduces intraglomerular pressure. This combined with osmotic diuresis leads to a reduction in volume overload, reduced blood pressure, and lower preload and afterload, which may have beneficial effects on cardiac remodelling and preserve renal function. Other effects include an increase in haematocrit and reduction in body weight.

The cardiac and renal benefits of dapagliflozin are not solely dependent on the blood glucose-lowering effect and not limited to patients with diabetes as demonstrated in the DAPA-HF and DAPA-CKD studies (29,30).

Dapagliflozin improves both fasting and post-prandial plasma glucose levels by reducing renal glucose reabsorption leading to urinary glucose excretion. This glucose excretion (gluretic effect), observed after the first dose, is continuous over the 24-hour dosing interval and is sustained for the duration of treatment. Thus, Dapagliflozin is administered one time per day (29-31).

The amount of glucose removed by the kidney through this mechanism is dependent upon the blood glucose concentration and GFR. Thus, in subjects with normal blood glucose, dapagliflozin has a low propensity to cause hypoglycaemia. Dapagliflozin does not impair normal endogenous glucose production in response to hypoglycaemia. Dapagliflozin acts independently of insulin secretion and insulin action. Improvement in homeostasis model assessment for beta cell function (HOMA beta-cell) has been observed in clinical studies with Dapagliflozin.

The SGLT2 is selectively expressed in the kidney. Dapagliflozin does not inhibit other glucose transporters important for glucose transport into peripheral tissues and is > 1,400 times more

selective for SGLT2 versus SGLT1, the major transporter in the gut responsible for glucose absorption (37,38).

